11. STATISTICAL CONSIDERATIONS

11.1 Sample Size Calculation

A priori power analysis was conducted to determine that we would have 80% power at alpha = .05 (two tailed) to detect a medium to large effect size with 12 participants in each group, leaving room for a 13% dropout rate. We therefore propose 20 participants per group.

11.2 Statistical Analysis

The main analysis will be a mixed factorial ANOVA to examine interaction effects between group (AET, SC, and HC) and time (pre- and post-) on measures of ERP, balance, BDNF and reaction time. If an interaction is found between group and time on any of the dependent variables (ERP, balance, BDNF and reaction time), the interaction will be explained using simple main effects. If no interaction is found for any of the dependent variable measures, the main effects for time and groups will be examined by a post hoc analysis to determine differences between groups. We anticipate greater change in the AET group compared to SC and HC group.

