5. STUDY DESIGN

5.1 Study Design

This study is designed as a randomized controlled trial. Potential PCS participants will be referred to another member of the research team by [name]. Potential participants will then complete the informed consent process and pre screening checklist. Potential healthy participants will contact the research team directly and set up a time to complete the informed consent, pre screening process, and IPAQ. After being deemed eligible based on the screening criteria (screening checklist attached, section), PCS participants will be randomly assigned to either an AET or standard of care (SC) intervention (see section 7). Using minimization software, each intervention group will be balanced by age and sex. Healthy participants will serve as the control group (HC) and will receive no treatment. Once participants in the SC group have completed the study, the AET will be offered, although it will not be included in the data analysis. Following informed consent, PCS participants will be provided with Garmin VivoSmart HR unit to monitor aerobic activity outside of the study (accelerometer, heart rate monitor, and step counter capabilities). Participants will be required to wear the Garmin units as often as possible for the duration of the study. In place of the Garmin VivoSmart HR unit, participants in the HC group will complete the IPAQ to determine physical activity levels prior to participating in the study,.

All participants will compete a series of pre and post intervention assessments (see section 7.2) over the course of one week at Lakehead University. Following the pre intervention assessments,

participants in the AET group will complete an eight week aerobic and balance retraining program at the School of Kinesiology, Lakehead University (see section 7.2). Participants in the SC group will continue with his/her standard of care for eight weeks. Healthy participants will be instructed not to significantly change his/her lifestyle (diet, physical activity) for the duration of the study weeks. After eight weeks, all participants will complete the assessments once again.

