6.4 Procedures for Participant Enrolment /Allocation /Randomization

To achieve adequate enrolment, recruitment flyers will be placed at several locations and clinics around Thunder Bay. Once informed consent has been obtained, and the potential participant has been deemed eligible through the screening process, age and sex of the participant will be used to randomly assign the participant to an intervention group through a process called minimization. This process ensures group sizes are equal and eliminates potential bias that may be introduced which is important for clinical research of small sizes. The NOSM research assistant would then communicate the enrolment and group assignment to [name] who will administer the AET intervention. The SC intervention will continue under the supervision of the participant's healthcare provider. Participants will be assigned a code number by the research assistant to ensure confidentiality is maintained during the transfer of data or samples between locations.

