going through regular standard of care and healthy control on measures of reaction time for dual and non dual tasking driving events. The analysis will be performed pre and post intervention to examine the interaction effect between group and time on measures of reaction time. The statistical analysis will include descriptive statistics to calculate means and standard deviation for each group for the pre and post test data. A mixed factorial analysis of variance will also be performed with group as the independent factor, time (pre and post intervention) as the repeated measure and reaction times as the dependent variable to examine the effect of the AET.

Preprocessing and analysis may either occur on [name] recording computer using asa-lab software or a separate analysis computer (also password protected) using EEGLab software. Prior to analysis data will be segmented into epochs around each event (trial) presentation. Data will be temporally filtered. Baseline line correction using the 200 ms before the stimulus presentation will be applied. Artifact detection and removal will be applied to remove trials that have been affected by excessive head motion (for example blinking, general body movement). Once preprocess, all the trials from the same condition type will be averaged to create an event-related potential for each condition type. This data, for each participant will be exported for statistical analysis (performed in JASP). Repeated measures ANOVA will be used to determine if there are significant between group and between condition differences.

Missing data will be handled according to the type of data that is missing. For analyses that depend on change (pre- vs post-), if a participant misses an assessment (i.e saliva) we will have to exclude the participant's results for that assessment. If the rest of the assessments were completed pre and post intervention, then they will be included in the data analysis.

There will be no interim analysis.

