12.2 Allocation sequence generation and concealment mechanism

To randomize participant group assignment, an online program called QMinim (<http://rct.mui.ac.ir/qminim/>) will be utilized. This program uses a process called minimization which ensures group sizes are equal and eliminates potential bias that may be introduced which is important for clinical research of small sizes (BMJ 2005;330:843).

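### AET and SC are minimised on age and sex, but no planned model includes either factor, so the randomised comparison is somewhat conservative wherever age or sex predicts change

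*Combined protocol and SAP*

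**What the plan says.** Section 5.1 describes the allocation of the symptomatic participants: "Using minimization software, each intervention group will be balanced by age and sex". Section 6.4 repeats it: "age and sex of the participant will be used to randomly assign the participant to an intervention group through a process called minimization". Section 12.2 names the software and gives the reason for the method: "This program uses a process called minimization which ensures group sizes are equal and eliminates potential bias". The healthy group (HC) is outside this scheme: "Healthy participants will serve as the control group (HC) and will receive no treatment" (Section 5.1).

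Age and sex are collected for everyone (Section 8.1 and the data abstraction form in 16.4).

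Three models are described, and none names a covariate:

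- Section 11.2, main analysis: "The main analysis will be a mixed factorial ANOVA to examine interaction effects between group (AET, SC, and HC) and time (pre- and post".
- Section 10, driving reaction time: "with group as the independent factor, time (pre and post intervention) as the repeated measure and reaction times as the dependent variable".
- Section 10, event-related potentials (ERP): "Repeated measures ANOVA will be used to determine if there are significant between group and between condition differences".

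The documents offer no other way of reflecting the minimisation, such as a re-randomisation test, and give no reason for leaving the factors out.

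**The concern.** Minimisation forces AET and SC to resemble each other in age and sex. If those factors predict the change in an outcome, the AET-SC difference varies less from trial to trial than it would under simple randomisation. A model with group and time alone does not register this. It leaves the age and sex variation in the residual and reports a standard error suited to an unbalanced design.

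The consequence is a test that rejects less often than its nominal level under the null, a confidence interval that is too wide, and precision that was obtained at allocation but does not show in the result. The plan chose minimisation because the trial is small, so an analysis that matches the allocation is the natural companion.

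**Working it through.** **Inputs from the documents.** 20 per group (5.2); 12 per group said to give 80% power at two-sided .05, with 13% dropout (11.1); ages 18-50 (4.4); minimisation on age and sex (5.1, 6.4).

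**Inputs not in the documents, hence assumed.** R², the share of the variance of change explained by age and sex together; the age bands; and the assignment probability of the minimisation program.

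**1. The plan's own figure.** Section 11.1 gives no numerical effect size. Read as a two-arm comparison of change, power depends on the noncentrality d × √(n/2) with 2n − 2 degrees of freedom.

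- n = 12: 80% power needs d = 1.20 (1.20 × √6 = 2.94).
- Evaluable after dropout: 20 × 0.87 = 17.4, about 17 per arm.
- n = 17: 80% power needs d = 0.99 (0.99 × √8.5 = 2.89).
- n = 17 and d = 1.20: noncentrality 3.50, power 92%.

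Both effect sizes are carried forward, because the plan does not decide between them. The step from 12 to 20 does not follow from 13% dropout (12/0.87 = 13.8, so 14). That is a separate matter and does not affect this point.

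**2. Why the standard error is too large.** With two visits, the group-by-time interaction is a comparison of change scores. Let σ² be the variance of change.

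- True variance of the AET-SC difference under complete balance: 2σ²(1 − R²)/n.
- Variance that the unadjusted model estimates: about 2σ²/n.
- Ratio of standard errors: 1/√(1 − R²), which is 1.05, 1.12 and 1.20 at R² 0.1, 0.2 and 0.3.

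With 32 degrees of freedom the critical value is 2.037. Multiplied by these ratios it becomes 2.147, 2.277 and 2.434, so the true rejection rate under the null is 4.0%, 3.0% and 2.1%. This is the limit. Real minimisation uses age bands and a random element, so the effect is somewhat smaller.

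**3. Simulation at 17 per arm.** 40 minimised on sex and two age bands with assignment probability 0.85, 6 lost at random, R² split equally between age and sex, 5,000 replicates. Entries are without vs with age and sex in the model. The last column comes from a separate run of 4,000 replicates.

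| R² | Type I error | Power, d = 0.99 | Power, d = 1.20 |
|---|---|---|---|
| 0 | | 80% vs 79% | |
| 0.1 | 4.2% vs 4.8% | 81% vs 83% | 92% vs 93% |
| 0.2 | 3.4% vs 4.8% | 81% vs 86% | 94% vs 96% |
| 0.3 | 3.3% vs 5.6% | 81% vs 91% | 95% vs 98% |

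Monte Carlo error is about 0.3 points for type I error and 0.5 for power. Another run gave unadjusted type I error of 4.2%, 3.4% and 2.6%, against 4.3% to 5.1% adjusted, so the 5.6% is simulation noise. A repeat at R² 0.3 and d = 0.99 gave 82% vs 90%, hence a range of about 2 to 9 points.

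**4. Checks on the cause.**

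- 20 per arm, three age bands, assignment probability 1.0: simulated ratios of estimated to true standard error are 1.05, 1.11 and 1.17 unadjusted, and 0.98 to 1.00 adjusted. At probability 0.8 the unadjusted ratios are 1.02, 1.11 and 1.12.
- Same design without minimisation: unadjusted ratio 0.98 to 1.02, type I error 5.0% to 5.4%. The excess therefore comes from balancing on factors that the model then omits.
- Age and sex affecting level only: ratio 0.99, type I error 5.1%. The effect cancels in change.
- Error term pooled with HC: the same ratios. For the three-group interaction, unadjusted type I error is about 3.6% to 4.7% across the runs, and the power gain about 3 to 9 points at d = 0.99.

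**The case against.** The strongest reply is that nothing is lost relative to the plan. Unadjusted power at d = 0.99 stays at about 81% against a target of 80%, and in the 20-per-arm runs it rises slightly with R². That stands. A reader might infer that the trial falls short of its planned power, or that minimisation is worthless unless the model uses it. Neither follows: balancing reduces the true variance whatever model is fitted, and only the reported standard error fails to show it.

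Second, the gain depends on the effect size. If Section 11.1 is taken at its word (80% at 12 per group, so d = 1.20), 17 per arm already has 92% power and adjusting adds only about 1 to 3 points. That also stands.

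Third, the planned test is a three-group interaction including an unrandomised group, whereas the calculation isolates AET against SC; the .05 level is stated only for the power analysis. This limits precision about the size, but the three-group interaction shows the same direction.

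Fourth, nothing in the documents shows that age or sex predicts eight-week change. Section 1 says that executive function and BDNF decline with age, and a reader might take that as support. It concerns level, which cancels in the group-by-time test. The simulation also generates and fits age linearly, which favours adjustment.

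**Conclusion.** The point holds as a low-severity improvement. Allocation uses age and sex, no stated model does, and where either predicts change the AET-SC comparison is conservative with an interval that is too wide.

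At an assumed R² of 0.1 to 0.3 and about 17 evaluable per arm, unadjusted type I error is about 4% to 3%, against about 5% adjusted. The forgone power is about 2 to 9 points at d = 0.99 and about 1 to 3 points at d = 1.20. These figures rest on assumed R², age bands and assignment probability. At R² = 0 there is no problem and no gain.

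The documents do not support reading this as bias in the treatment estimate or as a raised risk of a false positive: the error runs in the cautious direction.

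**What to change.** In Section 11.2 and in the Section 10 driving model, state that age (continuous) and sex are included as covariates of change because they are the minimisation factors. Either of two forms will do:

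- age-by-time and sex-by-time terms in the mixed ANOVA; or
- age and sex as covariates in a model of the change score.

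A main effect of age and sex alone is not enough in the mixed ANOVA, because it does not reach the within-subject error term that tests group by time.

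The ERP analysis needs its own wording, since Section 10 describes it by group and condition without time. Use the group-by-time model of Section 11.2 with the same terms. If a group-by-condition model without time is kept, enter age and sex as between-subject covariates.

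The cost is a sentence or two of analysis text and two degrees of freedom, which is about 1 point of power if age and sex are unrelated to change. No new data are needed. The wording should be fixed before outcomes are seen, so that the choice of covariates is not open to discretion.

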10. DATA / SPECIMEN ANALYSIS

[name] and the NOSM research assistant will be performing data analysis on the saliva samples at NOSM. [name], [name], [name], and [name] will be performing analysis on the physical and cognitive measures at Lakehead University. The main analysis will be a comparison of the pre- and post-outcomes.

[name] will perform the analysis of the data collected related to balance from the AMTI force platform and ImPACT neurocognitive assessment. The AMTI force platform measures the ground reaction forces that are generated by a body standing or moving across the plate. The AMTI force plate is also capable of measuring torques about each axis and has six degrees of freedom, which includes three forces (f_z , f_x , and f_y) and three moments (M_z , M_x , and M_y). All of these measures are fed into an AMTI amplifier and converted to digital signals via an analog to digital converter. The information collected by the force platform is then uploaded into BIOSOFT computer software which allows the researcher to view and analyze data following collection. The BIOSOFT computer software calculates the x and y moments of postural sway which are used to compute the variables of interest and produces graphical representations of this data. Descriptive statistics will be calculated to provide the mean and standard deviations for the variables of interest including the area of the centre of pressure, velocity of centre of pressure, length of centre of pressure, and displacement of centre of pressure. The main objective of the analysis is to compare pre- and post-treatment changes in balance. The ImPACT measures components of cognitive functioning including: attention, concentration, reaction time, memory, processing speed, decision making, problem solving, and response variability. The main objective of this component of the analysis will be to compare pre- and post-treatment changes in composite scores for the variables described.

[name] will perform the analysis on the data collected from the driving simulator. This analysis will include the comparison of people with concussion who will undergo AET to those

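### The plan names no AET-versus-SC test of change, and its rule after a null interaction does not estimate the treatment effect

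*Combined protocol and SAP*

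**What the plan says.** Section 5.1 randomises the concussed participants between AET and SC, using minimisation on age and sex. Healthy volunteers form a third group and receive nothing.

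Section 11.2 covers ERP, balance, BDNF and reaction time in one rule: "The main analysis will be a mixed factorial ANOVA to examine interaction effects between group (AET, SC, and HC) and time". If an interaction appears, "the interaction will be explained using simple main effects"; no direction or pair of groups is given. Otherwise, "If no interaction is found for any of the dependent variable measures, the main effects for time and groups will be examined", followed by post hoc comparison of the groups. The section closes with an expectation: "We anticipate greater change in the AET group compared to SC and HC group".

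Section 10 is less specific. It says "The main analysis will be a comparison of the pre- and post-outcomes", and for balance "The main objective of the analysis is to compare pre- and post-treatment changes in balance". For driving it compares AET with those "going through regular standard of care and healthy control on measures of reaction time for dual and non dual tasking driving events", using the same three-group model with "reaction times as the dependent variable to examine the effect of the AET". Its ERP sentence mentions groups and task conditions but not time.

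Among the hypotheses in section 2, items 2 (neural processing) and 5 (reaction time) name SC as comparator. Items 3 (balance) and 4 (BDNF) name none.

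**The concern.** AET versus SC is the only comparison protected by randomisation, and the plan does not say which result will answer it.

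- **The omnibus interaction** has 2 degrees of freedom over three groups. It can be significant because both concussed arms recover equally while healthy controls stay flat. Section 4.4 admits participants from two weeks after injury, so natural recovery over eight weeks is plausible.
- **Simple main effects** can mean group at one time point or time within one group. Group at post-test includes a valid AET-versus-SC comparison, but it ignores baseline. Time within AET includes recovery and practice.
- **After a null interaction**, the group effect averages pre and post values. That halves any benefit and carries the concussed-versus-healthy gap. The time effect pools change over all groups.

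For balance and BDNF, SC enters only through the general ANOVA of 11.2 and its closing expectation, so a within-AET reading is left open. At stake are lost power if the follow-ups are read pairwise, and shared recovery reported as benefit if they are read within AET.

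**Working it through.** **Inputs from the documents.** 20 per group (5.2, 11.1), two-sided alpha 0.05 and 13% dropout (11.1). The plan states no figure for an AET-versus-SC contrast, so there is none to reproduce.

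**Assumed inputs.** Outcome SD 1; pre/post correlation ρ of 0.3, 0.5 or 0.7; concussed groups starting 0.2 to 0.8 SD below HC; shared recovery of 0 to 0.8 SD; HC stable. Joint results come from simulation (20,000 replicates per null scenario, 10,000 per power scenario). Single tests were checked with noncentral F and t.

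**1. Interaction with no treatment effect.** Noncentrality = n(2/3)·rec²/[2(1−ρ)]. With n = 20, recovery 0.5 and ρ = 0.5 this is 20 × 0.667 × 0.25/1 = 3.33. On F(2,57) the interaction is significant in 34% of trials although AET equals SC.

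**2. Follow-ups with no treatment effect** (ρ = 0.5; range for ρ 0.3 to 0.7 in brackets).

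| Reading | Scenario | Frequency |
|---|---|---|
| Pairwise: AET-vs-SC t at post after an interaction, otherwise Tukey after a significant group effect | all 24 scenarios | 2.2–4.8% |
| Interaction and AET pre/post change both significant | recovery 0.25 SD | 5% (4–9%) |
| same | recovery 0.5 SD | 24% (16–45%) |
| same | recovery 0.8 SD | 68% (50–91%) |
| Null interaction, then significant time effect | recovery 0.25 SD | 21% (17–31%) |
| same | recovery 0.5 SD | 47% (42–47%) |
| Null interaction, then significant group effect | stable gap 0.5 SD | 41% (37–47%) |
| same | stable gap 0.8 SD | 80% (76–85%) |

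The pattern in which AET changes and SC does not occurs in 0.6–8%.

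Check of the last row: noncentrality = n(2/3)(gap − rec/2)²/[(1+ρ)/2] = 20 × 0.667 × 0.64/0.75 = 11.38, so the group effect is significant in 84.5%. It is independent of the interaction, which is null in 95% when there is no recovery: 0.845 × 0.95 = 80%.

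**3. Power for a true 0.8 SD benefit**, gap 0.8 SD, 20 per group. For the change score, noncentrality = 0.8 × √(20/2)/√[2(1−ρ)], which is 2.53 at ρ = 0.5 and gives 69% on 38 df. ANCOVA replaces the divisor by √(1−ρ²), with allowance for chance baseline imbalance.

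| AET-vs-SC analysis | ρ = 0.3 | ρ = 0.5 | ρ = 0.7 |
|---|---|---|---|
| Pairwise reading, no recovery | 56% | 61% | 67% |
| Pairwise reading, recovery 0.5 SD | 67% | 68% | 69% |
| Change score | 55% | 69% | 89% |
| ANCOVA on baseline | 72% | 80% | 93% |
| ANCOVA on baseline, age, sex | 70% | 78% | 91% |

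Recovery shared by both arms cancels in the last three rows.

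For a 0.5 SD benefit without recovery, the pairwise reading has 20/22/26% and ANCOVA with age and sex 34/40/55%. At 17 per group (20 × 0.87 = 17.4), a 0.8 SD benefit without recovery gives 46/51/58% against 61/70/85%.

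**4. Validity.** Type I error is 4.8–5.3% for the change-score contrast and for both ANCOVA models.

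**The case against.** The strongest reply is that the intent is clear. Section 11.2 expects more change in AET than in SC, hypotheses 2 and 5 name SC, and any ordinary post hoc procedure would include the AET–SC pair. Read that way there is no false-positive inflation. The larger percentages in step 2 are mostly detections of real recovery or a real concussed-versus-healthy gap, and they mislead only if called efficacy. No section says they will be. All of this stands, but an expectation is not a test. The pairwise reading is one the reader has to supply, and it costs power.

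Further points also stand:

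- The condition in 11.2 for moving to main effects can mean outcome by outcome, as assumed here, or only when every outcome is null. On the second reading the fallback is rarer. If one interaction is null 66% of the time, four independent ones are all null 0.66⁴ ≈ 19% of the time.
- HC is held stable here. Practice shared by all three groups would not trigger the interaction. The 0.8 SD recovery scenario assumes complete normalisation of a 0.8 SD gap.
- A change score does not always help. At correlation 0.3 with 0.5 SD recovery it has 55% power against 67% for the pairwise reading. ANCOVA with age and sex gains only 3 points there (70%).
- Including HC is not a fault in itself: hypothesis 2 uses them as a benchmark.

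**Conclusion.** The concern holds and should be fixed. The efficacy contrast is unspecified, and the stated rule after a null interaction does not estimate it. That conclusion follows from the contrasts themselves and needs no assumed numbers.

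The size does depend on assumptions. Read pairwise, the plan is safe against false claims. For a 0.8 SD benefit, ANCOVA with age and sex gains 14 to 24 points of power without recovery and 3 to 22 points with 0.5 SD recovery. Read as change within AET, a shared recovery of 0.5 SD would pass as benefit in 24% of trials (16–45%) when AET does nothing beyond SC. The plan does not commit to that reading, but it does not exclude it.

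**What to change.** In sections 10 and 11.2:

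- State that the treatment effect for ERP, balance, BDNF and reaction time is AET versus SC among randomised participants. Estimate it by ANCOVA of the post value on arm, baseline value, age and sex, with a 95% confidence interval, whatever the three-group interaction shows. A change-score contrast is also valid, but has less power.
- Remove the main-effects rule as a route to an efficacy conclusion.
- State that change within a group is not evidence of efficacy, and align the pre/post wording of section 10.
- Keep HC as a separate reference comparison for hypothesis 2.

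**Cost.** No new participants, visits or measures. Pre and post values are scheduled (7.1), age and sex are recorded (8.1), and section 10 already requires complete pre/post pairs for change analyses. Age and sex cost about 1.5 to 3 points of power if they carry no information.

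Section 11.1 should be revisited for the named contrast, because its effect size has no number and no stated comparison. The change does not settle how many measures are tested within each outcome. It also does not cover SCAT-3 and RPSQ, which hypothesis 1 uses but which appear in neither 7.1 nor 11.2.
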